10.2 Substudy 1 Introduction

[figure not shown]
Substudy 1 will evaluate the safety, PK, PD, and preliminary efficacy of AZD8853 monotherapy in participants with selected advanced/metastatic solid tumours and aims to define MTD/RP2D. For an overview of Substudy 1 design, see Figure 3.

10.3 Substudy 1 Objectives and Endpoints

Refer to Section 3 for the master objectives and endpoints applicable to all Substudies in the study. Details of Substudy-specific objectives and endpoints are provided in Table 15.

Table 15 Substudy 1 Objectives and Endpoints

Type	Objectives	Endpoints	
	Secondary		
PD	To evaluate the PD activity of AZD8853 by assessment of candidate biomarkers in participants with selected advanced/metastatic solid tumours (Part A and Part B only)	Change in circulating GDF15 serum levels	
PD	To evaluate the intra-tumoural PD activity of AZD8853 in participants with selected advanced/metastatic solid tumours (Part B only)	Change in CD8 tumour infiltrati by IHC using baseline and on-treatment samples	on
	Exploratory		
CCI	CCI	• CCI	
CCI	CCI	• CCI	
	CCI	- CCI	
CCI	CCI	• CCI	

10.4 Substudy 1 Study Design

10.4.1 Substudy 1 Design

In this Substudy of the FTiH, open-label, multicentre study, AZD8853 will be evaluated as monotherapy for safety, PK, PD, and preliminary efficacy in participants with selected advanced/metastatic solid tumours defined as:

- Second or later line setting of unresectable, locally advanced (Stage III) or metastatic (Stage IV) NSCLC that have progressed on anti-PD-1/PD-L1 inhibitors with or without platinum-containing chemotherapy.
- Third or later line setting of Stage IV MSS-CRC that have progressed on prior standard of care treatment.
- Second or later line setting of Stage IV UC that have progressed on prior treatment with platinum and/or checkpoint inhibitors.

The tumour types included in this study were selected based on unmet clinical need and underlying tumour biology. In both the dose-escalation (Part A) and dose-expansion (Parts B and C) parts of the study, participants with selected advanced/metastatic solid tumours who have progressed or are refractory to at least one line of standard therapy will be enrolled. These populations are thought to represent an unmet clinical need as currently available treatment options provide limited benefit. Moreover, internal investigation has revealed that NSCLC, MSS-CRC, and UC participants exhibit significantly higher serum GDF15 levels when compared to aged matched controls, and that higher serum GDF15 is correlated with a reduced overall survival (Mehta et al, 2015; Arfsten et al, 2019; and Traeger et al, 2019).

Participants will be followed until either death, loss to follow-up, withdrawal of consent or end of study. This Substudy of the study will comprise of 3 main parts (Figure 3), as follows:

Part A: Dose Escalation

The dose-escalation part of the study may enrol up to 45 participants (assuming up to 5 dosing cohorts and 3-9 participants per cohort) with selected advanced/metastatic solid tumours (NSCLC, MSS-CRC and UC). AZD8853 will be administered as monotherapy at the selected dose by i.v. infusion on a Q3W schedule. All participants will be treated until progressive disease, unacceptable toxicity, or withdrawal of consent.

See Section 10.6.6.1 for the starting dose, dose escalation and stopping criteria.

Part B: PD/MoA Expansion

Dose levels that are deemed safe in Part A of the study and have shown preliminary evidence of circulating free GDF15 reduction can be expanded in this PD/MoA expansion part of the study which will enrol up to approximately 20 participants with NSCLC and 20 participants with MSS-CRC advanced/metastatic solid tumours into 2 dose expansions (Part B1 and Part B2; approximately 10 NSCLC and 10 MSS-CRC participants in each part).

See Section 10.6.7 for details on PD/MoA expansion.

Mandatory archival, pre- and on-treatment tumour biopsies, serum GDF15 samples, and other samples including PK for each participant will be required at pre-specified timepoints. Pre- and on-treatment CD8+ PET imaging will be performed to assess PD response. Up to 10 participants in Part B1 and up to 10 participants in Part B2 will be enrolled with evaluable data from paired biopsies. Data from Part A and Part B of this Substudy of the study will inform tumour types and dose levels most suitable to progress onto an efficacy expansion part. The RP2D will be defined based on an updated PK/PD and safety analysis using data generated from both Part A and Part B of the study.

Cluster of Differentiation (CD)8+ Positron Emission Tomography (PET) Imaging

In Part B of the study, selected sites will use CD8+ PET imaging in combination with mandatory paired biopsies to monitor changes in CD8 T cell infiltration following treatment, to evaluate the correlation between the CD8 immune infiltrate present by IHC of biopsies with in vivo CD8 T cell localization by PET imaging using a ⁸⁹Zirconium (Zr)-deferoxamine (Df)-crefmirlimab.

Selected sites will recruit approximately up to 20 participants combined in Parts B1 and B2, across MSS-CRC and NSCLC study participants. These selected sites should prioritize recruitment to the CD8+ PET cohort of Part B prior to enrolling to non-CD8+ PET slots.

For further details on the CD8+ PET imaging, refer to Appendix I.

Part C: Efficacy Expansion

The efficacy expansion parts of the study will enrol up to approximately 40 participants in each expansion (Part C1 and Part C2). Relevant participants from Part B will count towards Part C efficacy expansions. These expansions may open either in parallel or sequentially at the Sponsor's discretion.

See Section 10.6.7 for details on efficacy expansion.

Mandatory pre- and on-treatment serum GDF15 samples and other samples including PK will be required. Archival of FFPE tissue is mandatory for all participants. Fresh pre- and on-treatment biopsies at pre-specified timepoints are CGI in this part of the study.

10.4.2 Substudy 1 Justification for Dose

A starting dose of 300 mg is proposed for AZD8853. The selection of the dose was based on the observed toxicology data from the cynomolgus monkey and a population PK model.

The HNSTD in non-human primate was estimated to be mg/kg following weekly doses with no toxicity concerns. Following AZD8853 administration, 100% reduction in serum GDF15 was observed with no apparent toxicity in animals. No changes in immunophenotyping and cytokine amounts were seen in the cynomolgus toxicology study. The observed Cmax and AUC₍₀₋₁₆₈₎ at mg/kg in cynomolgus monkey was CCI µg/mL and CCI µg*h/mL. Based on FDA Guidance for Industry: S9 Nonclinical Evaluation for anti-cancer Pharmaceuticals a starting dose was calculated. The mg/m², or a human equivalent dose of mg/kg. For a kg patient, this would equate to a CCI mg dose. An additional safety margin of color fold was applied to allow for a starting dose of 300 mg.

A population PK model was developed based on available PK and GDF15 data from cynomolgus monkeys. An allometric scaling, with an exponent of 0.85 for clearances and 1 for volume of distributions was applied to translate relevant PK parameters from animals to humans. A target turnover model was used to predict the percentage decrease in free GDF15 in serum (Lowe et al, 2009; Davda et al, 2010). At the proposed starting dose of 300 mg, the predicted Cmax and AUC_(0-168hr) in human were [CC] µg/mL and [CC] µg*hr/mL. Therefore a fold safety margin on Cmax and [CC] -fold safety margin on AUC_(0-168hr) is predicted.

At the proposed starting dose of 300 mg the model predicted a reduction of GDF15 at Cmax and C_{trough} of % and % respectively. Doses of 1000 and 3000 mg are expected to reduce free GDF15 levels by % and %, respectively at C_{trough}. A dose of 3000 mg is expected to have fold safety margins on Cmax and fold safety margins on AUC_(0-168hr). Although a relatively high suppression of GDF15 is expected at Cmax, the levels of GDF15 are expected to recover rapidly given the fast turnover of GDF15 in humans (3 hours [Xiong et al, 2017], or 24 minutes from cynomolgus monkeys). In addition, AZD8853 is not a T cell agonist or an innate immune agonist and GDF15 suppression is not expected to cause cascading immune-stimulatory effects. A cytokine release assay was not conducted as GDF15 is a soluble factor and is not expected to cause cross-linking of immune cells. No changes in immunophenotyping or cytokine analysis were seen during the 3-month cynomolgus toxicology study [Three Month Intravenous Toxicity Study Two Month Assessment of Recovery in the Cynomolgus Monkey (8447292)].

Overall given that AZD8853 has a clear safety profile in toxicological studies, relatively high safety margins based on both absolute dose and predicted human exposure and is not expected to cause cascading immune-stimulatory effects, a 300 mg dose is proposed as a first-in-human dose.

10.4.3 End of Substudy 1 Definition

The end of Substudy 1 is defined as the last scheduled visit or contact of the last participant enrolled in the Substudy.

10.5 Substudy 1 Population

Prospective approval of protocol deviations to recruitment and enrolment criteria, also known as protocol waivers or exemptions, is not permitted.

Main Consent

Informed consent must be obtained prior to any study specific assessments. After the participant signs the ICF, a participant enrolment number will be assigned.

Based on study design as outlined in Section 10.4.1, participants will be enrolled in the study.

The main ICF for participants in this Substudy will include consent (mandatory and optional) for all biomarker samples as outlined in the SoA (Table 12, Table 13, and Table 14).

10.5.1 Substudy 1 Inclusion Criteria

In addition to the master study inclusion criteria listed in Section 5.1, participants are eligible to be included in this Substudy only if the further Substudy 1 criteria below also apply:

- 1 Histologically or cytologically documented unresectable, locally advanced (Stage III) or metastatic (Stage IV) NSCLC, metastatic (Stage IV) MSS-CRC or metastatic (Stage IV) UC.
- 2 Participants must meet all of the tumour-specific criteria below, with documented progression from previous therapy at study entry. Interval progression between 2 lines of therapy defines separate lines of therapy. Both standard and investigational treatments will count as lines of therapy when determining eligibility.
 - (a) Participants with NSCLC must:
 - i. Have received at least one prior line of systemic therapy in the advanced/metastatic setting.
 - ii. Have received at least one prior line of therapy which contained an anti-PD-1/PD-L1 agent, with or without platinum-based chemotherapy.
 - iii. Have documented test results for:
 - Sensitizing EGFR mutations and ALK fusions/rearrangements
 - Other genomic alterations which are part of a local standard of care and for which a locally approved standard of care targeted therapy exists (such as ROS proto-oncogene 1 [ROS1] fusions/rearrangements, neurotrophic receptor tyrosine kinase (NTRK) fusions, RET fusions/rearrangements, MET exon 14 skipping mutations, BRAF V600E mutation, etc.).
 - iv. Have received targeted therapy according to the identified genomic alteration.

 Targeted therapy is not mandatory if it is not in the local standard of care, or if it is refused by the participant or contraindicated.
 - v. For Parts B and C: PD/MoA and Efficacy Expansions:

 No sensitizing EGFR mutations or ALK fusions/rearrangements (documented test result is mandatory).
 - (b) Participants with MSS-CRC:
 - i. Must have documented MSS by local testing (genetic analysis or immunohistochemistry).
 - ii. Must have received at least 2 prior lines of systemic therapy for advanced/metastatic disease.
 - Prior systemic therapies must include fluoropyrimidines, irinotecan and oxaliplatin, unless refused or contraindicated. Participants may or may not have received a vascular endothelial growth factor (VEGF) agent (eg, bevacizumab), a BRAF inhibitor and an EGFR therapy (eg, cetuximab or panitumumab), according to local standard or care.
 - iii. Participants who have withdrawn from standard treatment due to unacceptable toxicity warranting discontinuation of treatment and precluding retreatment with the same agent prior to progression of disease will be eligible to enter the study.

- iv. Participants who had received adjuvant chemotherapy and had recurrence during or within 6 months of completion of the adjuvant chemotherapy are allowed to count the adjuvant therapy as one prior line of chemotherapy.
- (c) Participants with UC must:
 - i. Have histological confirmation of unresectable, locally advanced or metastatic UC (including any of the following: renal pelvis, ureters, urinary bladder, and/or urethra). Histological confirmation at initial diagnosis is acceptable. Participants must have received at least one prior line of systemic therapy including prior platinum-containing regimen and/or a checkpoint inhibitor therapy with anti-PD-1 or anti-PD-L1.
- 3 Participation in a clinical trial is determined to be the best option for next treatment based on prior response and/ or tolerability to standard of care in the opinion of the Investigator.
- 4 Participants must provide archival tumour tissue (FFPE block or unstained slides if a block cannot be provisioned). Refer to Section 10.8.6.2 and the Laboratory Manual for additional details.

Part B only:

- 5 All participants must be willing to provide mandatory paired biopsies (pre and on-treatment biopsies). The biopsied lesion must be distinct from any lesion used in the RECIST v1.1 evaluation.
- 6 CD8+ PET Cohort Only: Participants must have at least one non-liver lesion, suitable for PET imaging and be willing to be assessed with CD8+ PET imaging at screening (pre-treatment) and designated on treatment timepoints.

10.5.2 Substudy 1 Exclusion Criteria

In addition to the master study exclusion criteria listed in Section 5.2, participants are excluded from this Substudy if any of the further Substudy 1 criteria below also apply:

- 1. Participants who have received prior immunotherapy with anti-PD-1, anti-PD-L1, or anti-CTLA-4:
 - a) Must not have experienced a toxicity that led to permanent discontinuation of prior immunotherapy.
 - b) All AEs while receiving prior immunotherapy must have completely resolved or resolved to baseline prior to screening for this study.
 - c) Must not have experienced a ≥ Grade 3 imAE or a neurologic or ocular imAE of any grade while receiving prior immunotherapy. Note: Participants with an endocrine AE of ≤ Grade 2 are permitted to enrol if they are stably maintained on appropriate replacement therapy and are asymptomatic.

- d) Must not have required the use of additional immunosuppression other than corticosteroids for the management of an AE, not have experienced recurrence of an AE if re-challenged, and not currently require maintenance doses of > 10 mg prednisone or equivalent per day.
- 2. Participants with spinal cord compression or history of leptomeningeal carcinomatosis.
- 3. Participants with brain metastases unless treated, asymptomatic, stable, and not requiring continuous corticosteroids at a dose of > 10 mg prednisone/day or equivalent for at least 4 weeks prior to the start of the study.
- 4. Exclusion criteria for participation in the study include:
 a) CCI
 b) CCI

10.6 Substudy 1 Study Intervention

10.6.1 Study Intervention(s) Administered

10.6.1.1 Investigational Products

Please refer to Section 6.1 for AZD8853 details.

10.6.1.2 Investigational Imaging Agent

Imaging sites will be provided with an investigational imaging agent (Part B only), an anti-CD8 minibody (Mb) (Crefmirlimab) conjugated with Df and radiolabelled with Zr-89 (⁸⁹Zr-Df-crefmirlimab), for participants in the CD8+ PET imaging cohorts (see Appendix I for more details).

10.6.2 Preparation/Handling/Storage/Accountability

Please refer to Section 6.2 for details on preparation/handling/storage/accountability of study intervention.

10.6.3 Measures to Minimise Bias: Randomization and Blinding

Please refer to Section 6.3 for details on randomisation and blinding.

10.6.4 Study Intervention Compliance

Please refer to Section 6.4 for details on study intervention compliance.

10.6.5 Concomitant Therapy

Please refer to Section 6.5 for details on concomitant therapy.

10.6.6 Dose Modification

Discontinuation or withholding of study intervention will be implemented to manage potential immune-related and non-immune mediated AEs based on severity of treatment-emergent toxicities graded per NCI CTCAE v5.0. Dose reductions are not permitted. For any \geq Grade 3 AE that does not meet criteria for treatment discontinuation and whose causal relationship is attributable to the IMP, a single scheduled dose of IMP may be skipped (maximum of 2 non-consecutive doses) to permit resolution and the next dose will be administered on the next scheduled date. Omitted doses will not be administered at a later date. If the toxicity does not resolve to \leq Grade 1 or baseline by the time of the next scheduled dose after skipping one dose of IMP (ie, a total of 2 consecutive doses are skipped), the participant will be permanently discontinued from treatment.

Potential risks for AZD8853 are expected to be similar to those of other human monoclonal immunoglobulins, and include immune-mediated and non-immune-mediated risks. The overall dose modifications, are given below:

- Grade 1 No dose modification.
- Grade 2 Hold study intervention until resolution to Grade ≤ 1 or baseline.
 - If toxicity worsens, then treat as Grade 3 or Grade 4.
 - Study intervention can be resumed once event stabilises to Grade ≤ 1 .
 - Consider whether study intervention should be permanently discontinued in Grade 2 events with high likelihood for morbidity and/or mortality when they do not rapidly improve to Grade < 1 upon treatment.
- Grade 3 Hold study intervention (see rules for Grade 2 events), or permanently discontinue as per AZD8853 TMG.
- Grade 4 Permanently discontinue study intervention.

For detailed guidelines on management of toxicities and dose modifications (temporary or permanent discontinuation only) refer to AZD8853 TMGs provided to the sites as a separate document.

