###### Substudy 1:

- Duration of exposure is defined by last date of actual dosing (i.e., a dose  $> 0$  [mg] is given) in the last cycle plus 21 days minus the date of first treatment with IP plus 1 day.
  - For participants who die whilst on study treatment or if a DCO occurs, duration of exposure is defined as date of death/DCO (whichever occurs first) minus the date of first treatment plus 1 day.
  - Therefore: Duration of exposure(days) = (min (last dose date where dose  $> 0$  [mg] + 21 days, date of death, date of DCO) – first dose date + 1).
- The duration of exposure in cycles is calculated as:

Duration of exposure (cycles)= The number of cycles in which at least one portion of IP was administered (i.e., dose  $> 0$  [mg])

If a cycle is prolonged due to toxicity, this should still be counted as one cycle.

- The actual duration of exposure is calculated as:

Actual duration of exposure

(days)= Number of cycles participants received X 21 (days)

Duration of exposure is calculated as above, and dose interruptions are defined as any length of time where the participant has not taken any of the planned dose in accordance

with the protocol. The actual exposure calculation makes no adjustment for any dose reductions that may have occurred.

- Dose intensity of IP(s) is addressed by considering relative dose intensity (RDI), where RDI is the percentage of the actual dose delivered relative to the intended dose through to treatment discontinuation. More specifically, RDI is defined as follows:

$$RDI = 100 \times d/D$$

- where d is the actual cumulative dose delivered up to the actual last day of dosing and D is the intended cumulative dose up to the actual last day of dosing. D is the total dose that would be delivered if there were no modification to dose or schedule.
- Percentage of first dose received, which is used to define the DLT population is calculated as

$$\text{Percentage of dosing received} = \frac{\text{Actual first dose of AZD8853 received}}{\text{Planned first dose of AZD8853 received}} * 100$$

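### For drug-related Grade 3 events, protocol Section 10.6.6 holds two unreconciled hold-and-stop texts, so who counts as an adverse event leading to discontinuation depends on which one a site follows

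*Protocol*

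**What the plan says.** Protocol Sections 4.1.1 and 7.1.1 leave dose modification and the criteria for stopping and restarting to each Substudy. For Substudy 1 that is Section 10.6.6, which has two relevant parts.

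**Opening paragraph.** It applies to adverse events of Grade 3 or higher "that does not meet criteria for treatment discontinuation and whose causal relationship is attributable to the IMP". For these, "a single scheduled dose of IMP may be skipped (maximum of 2 non-consecutive doses) to permit resolution". Dosing then continues on the next scheduled date, and "Omitted doses will not be administered at a later date". If the event is not back to Grade 1 or lower, or to baseline, by the next scheduled dose after one skip, the consequence is mandatory: "ie, a total of 2 consecutive doses are skipped), the participant will be permanently discontinued from treatment".

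**List by grade.** For Grade 3 it says: "Hold study intervention (see rules for Grade 2 events), or permanently discontinue as per AZD8853 TMG". The Grade 2 rule that this brings in is: "Hold study intervention until resolution to Grade ≤ 1 or baseline". Its restart sub-bullet reads "Study intervention can be resumed once event stabilises to Grade" 1 or lower, without mentioning baseline. Grade 4 means permanent discontinuation. The section ends by referring sites to the AZD8853 toxicity management guideline (TMG), a separate document, for detail.

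The incidence of adverse events leading to discontinuation of AZD8853 is listed under the primary safety objective (Protocol Section 3, Table 4). SAP Table 3 classes it as primary, on the safety analysis set.

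**The concern.** Both parts apply to a Grade 3 event attributed to the drug that does not already meet discontinuation criteria. The paragraph sets a limit and a mandatory stop. The bullet gives a hold that ends at resolution, with no count of missed doses and no tie of the restart to a scheduled date. No sentence says which governs or that one qualifies the other.

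In a multicentre first-in-human study, two sites could therefore handle the same toxicity differently while each follows a sentence of the protocol. Participant management is at stake first. The count of discontinuations due to adverse events, a primary component, then depends on local reading as well as on tolerability. Exposure and relative dose intensity also follow from which doses are given.

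**Working it through.** The plan gives no figure to reproduce. The check sets the two texts side by side on the dosing calendar.

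**Inputs**
- Dosing every 3 weeks (Protocol Section 10.4.1), so scheduled doses fall on Day 1 + 21k: Days 1, 22, 43, 64, 85.
- The two texts of Section 10.6.6 as set out above.
- Group sizes: 9 (maximum per escalation cohort, Section 10.6.6.1.3), 20 (approximate size of each Part B dose level, and the Part C interim, Sections 10.6.7 and 10.9.5), 40 (each Part C expansion, Section 10.9.2).

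**Scope of the overlap**
- Grade 4: the list stops treatment, so there is no hold to compare.
- Grade 3, not attributed to the drug: only the list applies.
- Grade 3, attributed to the drug, not already meeting discontinuation criteria: both texts apply.

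**Trace.** Last dose on Day 1, such a Grade 3 event starting before Day 22. Resolved here means Grade 1 or lower, or baseline.

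| Resolved | Opening paragraph | Grade 3 bullet through the Grade 2 rule |
|---|---|---|
| By Day 22 | Dose on Day 22 | Dose on Day 22 |
| Days 23 to 43 | Skip Day 22, dose on Day 43 | Hold; Day 43 allowed, but the restart is not tied to that date |
| After Day 43, for example Day 50 | Permanent stop at Day 43 | Hold may continue; next scheduled dose Day 64, unless the TMG or the investigator stops treatment |

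The outcomes separate only in the last row, when the event is unresolved at the second scheduled dose, 43 − 1 = 42 days after the last dose.

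**Lesser differences.** The paragraph allows at most two skips, not in succession; the list gives no total. The restart sub-bullet omits baseline, although its parent bullet includes it; this matters only for someone whose baseline grade is above 1.

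**Effect on the primary component.** One participant counted differently moves the incidence by 100/n points:
- n = 9: 100/9 = 11.1
- n = 20: 100/20 = 5.0
- n = 40: 100/40 = 2.5

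The documents give neither the frequency of such events nor their time to resolution, so the expected number of participants affected cannot be calculated.

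**Effect on the MTD.** DLTs are events in the 21 days of Cycle 1 (Section 10.6.8). The MTD comes from isotonic regression on DLT rates (Section 10.6.6.1.3; SAP Section 4.2.1.8.1). The texts part at Day 43 at the earliest, after that window. One DLT criterion refers to a disruption of dosing of more than 21 days, but an event unresolved at Day 43 keeps the participant off dosing on that day under both texts, so it does not separate them.

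**The case against.** The strongest reply is that the two texts can be read together. The list never says that a hold is unlimited; it is silent. The paragraph is the more specific rule for drug-related events of Grade 3 or higher, and its wording is mandatory, whereas the list only permits a restart. A site that obeys every sentence would hold, then stop if a second consecutive dose would be missed. The TMG, which cannot be seen here, may state the limit as well. This reading is reasonable. However, the protocol does not state it, and the bullet points to the Grade 2 rule and the TMG, not to the paragraph above it. What stands is that the defect is missing precedence, not two irreconcilable rules.

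Four stronger inferences are tempting, and the documents do not support them.
- *That nobody need be discontinued under the bullet.* The bullet also offers permanent discontinuation under the TMG, and Section 7.1 lets a participant be discontinued for an adverse event.
- *That dose selection is distorted.* The MTD is not affected, as shown. The RP2D draws on PK/PD and safety data from Parts A and B (Section 10.4.1), but no rule links it to the incidence of discontinuation.
- *That a large share of Grade 3 events is affected.* Any percentage would rest on assumed resolution times in a subset of unknown frequency.
- *That the SAP shows the conflict.* Its exposure section says "If a cycle is prolonged due to toxicity, this should still be counted as one cycle". This fits a Grade 2 hold, to which the paragraph does not apply. It also fits a longer interval after a skipped dose, since only cycles with some drug given are counted.

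The endpoint is also descriptive: Substudy 1 states no hypotheses (Section 10.9.1) and makes no direct comparison between cohorts (Section 10.9.4.1).

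**Conclusion.** The point holds within a narrow scope. For Grade 3 events attributed to AZD8853 that do not already meet discontinuation criteria, Section 10.6.6 leaves open whether a participant still unresolved at the second scheduled dose must stop or may stay on hold. Each such participant counts towards a primary safety component under one text and may not under the other. The shift per participant is material in an escalation cohort of 9 and modest in an expansion of 40; the total is unknown.

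The conclusion rests on the protocol text alone, on dosing staying on the 3-week calendar, and on the TMG being unavailable. A limit in the TMG would reduce the practical divergence but would not supply the missing precedence in the protocol. No view is taken on which rule is right.

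**What to change.** Reconcile the opening paragraph, the Grade 2 and Grade 3 bullets and the TMG into one statement of how they interact. It should cover:
- what limit, if any, applies to a hold, and for which events;
- whether dosing restarts only on a scheduled date or once the event has resolved;
- one restart level, worded the same way each time.

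The choice of rule belongs to the sponsor and its safety physicians. Then check that the SAP definitions of cycle, delay, interruption and exposure (Sections 4.2.1.1.1 and 4.2.1.1.2) match the reconciled text, and change them only if they do not.

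The cost is wording in the next protocol amendment, a check of the TMG and a short check of the SAP. It needs no additional participants, visits or procedures.
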